# Post-transplant thrombotic microangiopathy

Incidence of post-transplant thrombotic microangiopathy (TMA) by 6 months post-randomization. TMA definition is provided in section 2.5.3.3.

# 3.3.6. CMV-reactivation

Proportion of patients requiring new systemic treatment for an increasing CMV PCR level per institutional practice (patients receiving only standard of care viral prophylaxis will not be included in this assessent) for CMV-reactivation by Day 56 post-randomization.

# **3.3.7.** Patient-reported Outcomes

These instruments will be completed by patients at enrollment, Day 56, 6 months, and 12 months. Only English speaking adult and pediatric patients, and Spanish speaking adult patients are eligible to participate in the Health Quality of Life (HQL) component of this trial. Patients >18 years will complete the FACT-BMT, MOS SF-36 and MDASI instruments. Patients ≥ 8 years through 18 years will complete the PedsQLTM Stem Cell Transplant Module. Surveys are completed by participants using self-completed instruments as a first choice. If this method of data collection is not possible, then surveys and response options may be read verbatim to participants, either in person or over the phone, to collect data. The method of survey completion, the date, and the language will be recorded in the database. Surveys may not be completed by surrogates.

Change in patient-reported outcomes from enrollment to Day 56 and 6 months will be calculated.

### a. MD Anderson Symptom Inventory (MDASI)

The MDASI is a 19 item instrument that captures 13 symptoms (0="not present" to 10="as bad as you can imagine") and 6 items measuring interference with life from 0 ("did not interfere") to 10 ("interfered completely"). It provides two summary scales: symptoms and interference. The MDASI will be scored according to the recommendations of the developers. We estimate it will take 5 minutes to complete the MDASI. Surveys are completed by participants using self-completed instruments as a first choice. If this method of data collection is not possible, then surveys and response options may be read verbatim to participants, either in person or over the phone, to collect data. Surveys may not be completed by surrogates. b. FACT-BMT

The FACT-BMT, Version 4 is a self-administered instrument designed to assess multidimensional aspects of the QOL in BMT patients. It consists of the 27-item FACT-General (FACT-G) and the 23-item Bone Marrow Transplantation Subscale (BMTS). The FACT-G assesses four primary dimensions of QOL, including physical well-being (7 items), social/family well-being (7 items), emotional well-being (6 items), and functional well-being (7 items). A five point Likert-type response scale ranging from 0 to 4 is used (0 = 'not at all'; 1 = 'a little bit'; 2 = 'somewhat'; 3 = 'quite a bit'; and 4 = 'very much'). The original FACT-BMT was developed in English using a standardized approach for item derivation, reduction and testing, and has been used extensively in various clinical trials. The FACT-BMT has since been translated into other languages.

#### c. MOS Short Form 36 (SF-36)

The MOS SF-36 Version 2 is a 36-item self-report questionnaire which assesses patient-reported health and functioning. The instrument examines the following domains of QOL: physical functioning (PF), role functioning-physical (RP), bodily pain (BP), general health (GH), vitality (VT), social functioning (SF), role functioning-emotional (RE), and mental health (MH). Two summary scales from the SF-36 include the physical component score (PCS) and the mental component score (MCS).

# d. PedsQL

The PedsQL measurement model for pediatric quality of life inventory is a multi-dimensional tool for monitoring health-related quality of life (HRQOL) in children and adolescents (age 2-18). Age-specific versions for younger and older children are available. Physical, emotional, social, and school functioning are assessed. The PedsQLTM Stem Cell Transplant Module is a 46 item instrument that measures health-related quality of life in children and adolescents undergoing hematopoietic stem cell transplant, and is developmentally appropriate for self-report in ages 8 through 18 years.

# 3.3.8. AA3 Biomarker Outcomes

A secondary descriptive analysis will evaluate outcomes for AA3 patients. Patients with a missing AA result will be excluded.

# CHAPTER 4

### 4. PATIENT ENROLLMENT AND EVALUATION

#### 4.1. Approaching Patients, Eligibility Screening and Obtaining Consent

Patients with previously untreated, standard-risk acute GVHD, according to the refined Minnesota Criteria, who are in need of systemic therapy, will be approached as soon as possible. Patients willing to participate in the trial will sign an Institutional Review Board approved consent form. Physicians will further evaluate each patient's eligibility for randomization onto this study (see Section 2.4).

#### 4.2. Enrollment/Randomization

Patients will be enrolled/randomized onto the study using the BMT CTN Advantage Electronic Data Capture (EDC). Patients will be randomized to Sirolimus versus Prednisone in a 1:1 ratio. The following procedures shall be followed:

- 1. An authorized user at the clinical center completes the initial screening by entering patient demographics and Segment A information (consent date, inclusion/exclusion criteria and confirmation that 5 mL of blood has been collected for Ann Arbor Scoring) on the Eligibility Form.
- 2. If the patient is eligible, a study number and random treatment assignment is generated.
- 3. A visit schedule based on enrollment date is displayed for printing.
- 4. Immediately after randomization, the 5 ml blood sample will be shipped priority overnight for early morning arrival at the Biomarker Laboratory of the Icahn School of Medicine at Mount Sinai for biomarker analysis.

If a connection is interrupted during a randomization session, the process is completely canceled and logged. A backup manual registration and randomization system will also be available to provide for short-term system failure or unavailability.

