#### **PROTOCOL SYNOPSIS – BMT CTN PROTOCOL 1501**

### A Randomized, Phase II, Multicenter, Open Label Study Evaluating Sirolimus and Prednisone in Patients with Refined Minnesota Standard Risk, Ann Arbor 1/2 Confirmed Acute Graft-Versus-Host Disease

Co-Chairs:	[name], PhD and [name]	
Study Design:	The study is a Phase II randomized, open label, multicenter trial designed to identify whether sirolimus is a potential alternative to prednisone as an up-front treatment for patients with standard-risk acute GVHD defined according to clinical and biomarker-based risk stratification.	
	Patients with previously untreated, standard-risk acute GVHD, according to the refined Minnesota Criteria, who are in need of systemic therapy, will have a 5 mL blood sample collected prior to randomization to assess their biomarker Ann Arbor Risk status. Ann Arbor scoring results will be provided 48-72 hours after randomization. Patients will begin their study treatment assignments within 24 hours of randomization. Those with biomarker results of combined AA1/2 risk will continue on their randomized study treatment and will be included for primary endpoint analysis and all planned study procedures and assessments. In contrast, patients with AA3 biomarker risk and those patients with missing biomarker results may continue on their physicians' discretions. In addition, AA3 risk patients and those with missing results will not be considered in primary endpoint analysis, but will be included in a subset analysis.	
Primary Objective:	The primary objective is to assess the rate of complete remission (CR)/partial remission (PR) on day 28 post-randomization in patients with standard-risk acute GVHD defined by both clinical and AA1/2 risk status.	
Secondary Objectives:	Secondary objectives are to assess the following:	
	
 
The proportion of patients with an acute GVHD response on Day 28 (CR or PR) and who are on a prednisone (or prednisone dose-equivalent corticosteroid) dose of 0.25mg/kg/day or less.
 
Proportions of CR, PR, mixed response, no response and progression among surviving patients at Day 14, 28 and 56.
 
Treatment failure (treatment failure defined as: no response, progression, administration of additional therapy for GVHD
 
	

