- 8. Biopsy confirmation of GVHD is not required. Enrollment should not be delayed for biopsy or pathology results unless local institutional practice mandates biopsy confirmation to make a GVHD treatment decision.
- 9. Written informed consent and/or assent from patient, parent or guardian.
- 10. Collection of a 5 ml blood sample (red top for serum) from the patient for Ann Arbor Scoring and ready to be shipped immediately after randomization.

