# 2.5. Treatment Plan

#### 2.5.1. Randomization

A 5 mL blood sample (red top tube) for Ann Arbor Scoring must be collected from the patient prior to enrollment/randomization in AdvantageEDC (see section 2.5.2). Upon confirmation of eligibility in AdvantageEDC, the study participant will be randomized in a 1:1 fashion to receive either sirolimus or prednisone. Study treatment (sirolimus/prednisone) should be initiated as soon as possible after randomization. A maximum of 24 hours from randomization to first dose of study medication is allowable.

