#### 2.5.2. Ann Arbor Scoring

Immediately after randomization, the 5 ml of blood (red top for serum) will be shipped priority overnight for early morning arrival at the Biomarker Laboratory of the Icahn School of Medicine at Mount Sinai for biomarker analysis. Samples can be shipped Monday to Friday, and results can be delivered Tuesday through Saturday. Once received in the laboratory, the GVHD biomarkers used to assign the Ann Arbor GVHD score will be measured by ELISA using standard technical procedures in a CLIA certified laboratory. Processing the sample, measuring, and confirming the ELISA assay results take 4.5 hours (range 4-6 hours). Once the Ann Arbor

score is confirmed, the investigator at the participating center will be notified if the patient has AA1/2 biomarker risk, AA3 biomarker risk or missing biomarker results. Notification of the patient's Ann Arbor results will occur within 72 hours of study enrollment/randomization (usually within 48 hours).

Those with AA1/2 status will remain on their randomized therapy. AA3 patients and patients with missing biomarker results can continue on their randomized therapy, or another therapy, per the discretion of the treating physician. All patients, regardless of treatment received or biomarker status, must complete all planned study assessments. Patients with AA1/2 biomarker status and clinical standard risk will be included in the analysis for the primary endpoint. In contrast, patients with AA3 status or missing biomarker status will not be considered for the primary analysis, but will be included as a secondary descriptive analysis. GVHD response and therapy used in patients with AA3 status may be used in exploratory analyses to generate hypotheses for future high risk GVHD trials.

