### 5.2.4. Analysis of Primary Endpoint

The difference in Day 28 CR/PR rates between arms will be estimated along with a 90% confidence interval. Note that patients classified as high risk per biomarker results and patients with missing biomarker results will be excluded from the primary analysis. In addition to the difference in rates, within arm CR/PR rates will be estimated with accompanying confidence intervals.

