## 2.8 Analysis Populations

### 2.8.1 Primary Analysis Population

Participants will be analyzed according to the intent to treat (ITT) principle for this study, i.e. according to the treatment groups to which they were randomized, regardless of whether the assigned treatment was administered. Any participant who receives a treatment randomization number will be considered to have been randomized. Since the primary interest of this study is treatment in participants with standard risk acute GVHD, the primary analysis population will consist of all randomized AA1/2 participants with treatment classified per the ITT principle.

The primary analysis for the primary, secondary, and exploratory endpoints will use the primary analysis population. A secondary analysis of the primary endpoint will be

performed, classifying participants by the initial treatment actually given. Another secondary analysis will consider primary and key secondary outcomes for all randomized AA3 participants classified per the ITT principle. An analysis of safety endpoints will also be conducted using the safety analysis population as described below. Analyses of each endpoint and population used will follow the analysis plan as described below in section 4 of this SAP.

If a participant is deemed not eligible for the study after study registration or randomization occurs, he will be excluded from all analysis populations.

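### The site ships the Ann Arbor sample only after the open-label arm is known, so whether a patient has a score, and stays in the primary analysis, can depend on the arm; no planned analysis shows the effect on the estimate.

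*Protocol*

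**What the plan says.** **Order of steps.** The tube "must be collected from the patient prior to enrollment/randomization in AdvantageEDC" (Protocol 2.5.1), and inclusion criterion 10 asks that it be "ready to be shipped immediately after randomization". In Protocol 4.2, Segment A of the eligibility form confirms only that the blood was collected. Step 2 then reads: "If the patient is eligible, a study number and random treatment assignment is generated". Step 4 reads: "Immediately after randomization, the 5 ml blood sample will be shipped priority overnight for early morning arrival at the Biomarker Laboratory". Section 2.5.2 and Appendix B give the same order, and Appendix B adds that shipping is on the day of collection. The synopsis describes the design thus: "The study is a Phase II randomized, open label, multicenter trial".

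**What a missing result does.** Protocol 2.5.2 states: "AA3 patients and patients with missing biomarker results can continue on their randomized therapy, or another therapy, per the discretion of the treating physician"; section 4.2.1 agrees. Protocol 5.2.4 adds that "patients with missing biomarker results will be excluded from the primary analysis", and 5.1.3 extends this to the secondary endpoints. SAP 2.8.1 has the same effect: "the primary analysis population will consist of all randomized AA1/2 participants". Neither document defines a missing result.

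**What is checked.** The SAP's baseline shell (Exhibit 1501-2) has a row for missing Ann Arbor status by arm. SAP 3.2 plans a consort diagram and a list of significant deviations showing treatment assignment. The sensitivity analysis in SAP 2.2 concerns missing Day 28 response, not missing biomarker results.

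**A conflict.** The synopsis and Protocol 2.5.2 and 5.1.3 say that patients with missing results will be covered in a subset or secondary analysis. Protocol 3.3.8 and 5.2.7 and SAP 4.3.11 leave them out of the AA3 analysis, and no other analysis is specified for them.

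**The concern.** The score comes from blood drawn before randomisation, so among assayed samples the split between AA1/2 and AA3 should not depend on the arm. The existence of a score is different. It is settled after the assignment is known, partly by people who know it, and its absence has two consequences at once: the patient leaves the analysis, and the choice of therapy is freed.

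If missing results are more frequent in one arm, and those patients respond differently from the rest, the estimated difference is biased. Classifying the remaining AA1/2 patients by assigned arm cannot correct for who was left out, and the confidence interval would not reveal it. That estimate is the trial's main product, since the protocol plans no formal test.

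**Working it through.** **Inputs from the documents.** 150 randomised 1:1 (75 per arm); 60 analysed per arm; assumed response 60% in each arm, or 50% on sirolimus against 60% (Protocol 5.1.5); 90% Wald interval (SAP 4.1); about 30 AA3 patients expected (Protocol 5.2.7).

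**1. The plan's own figure.** The lower bound is (pS − pP) − 1.645 × sqrt[pS(1 − pS)/n + pP(1 − pP)/n].
- 60% v 60%, n = 60: 0 − 1.645 × sqrt(2 × 0.6 × 0.4/60) = −14.7% (printed −15%).
- 50% v 60%, n = 60: −0.10 − 1.645 × sqrt((0.25 + 0.24)/60) = −24.9% (printed −25%).

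Both are reproduced. The half-width at equal rates is 14.7 points.

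**2. The missing rate.** The number randomised is 120/(1 − 0.20) = 150, where the 20% covers AA3 plus missing results. The 30 expected AA3 patients are already 30/150 = 20%, which leaves 150 − 120 − 30 = 0 for missing results. The documents therefore supply no usable rate, and the counts in step 3 are assumptions.

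**3. Possible shift.** Suppose that 60 sirolimus patients are analysed with 36 responders (60%), that k more are unscored and respond at rate q, and that none is missing on prednisone. The shift in favour of sirolimus is 36/60 − (36 + kq)/(60 + k).

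| k | q = 60% | q = 40% | q = 0% |
|---|---|---|---|
| 2 | 0 | 36/60 − 36.8/62 = 0.6 points | 36/60 − 36/62 = 1.9 points |
| 4 | 0 | 36/60 − 37.6/64 = 1.3 points | 36/60 − 36/64 = 3.8 points |
| 6 | 0 | 36/60 − 38.4/66 = 1.8 points | 36/60 − 36/66 = 5.5 points |

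Against the half-width, the largest shift at q = 40% is 1.8/14.7 = 12%, and the largest at q = 0% is 5.5/14.7 = 37%. If the missing results were all on prednisone, the direction would reverse.

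**4. Precision.** With AA3 at 20% and an assumed missing rate m in both arms, n per arm is 75 × (1 − 0.20 − m). For m = 2%, 5% and 10%, n is 58.5, 56.3 and 52.5, and the lower bound at equal rates is −14.9%, −15.2% and −15.7%. The loss of precision is small; the issue is bias.

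**The case against.** The opportunity is narrow. The tube is already drawn and ready, and same-day shipping is instructed. At that moment the site has not seen the Day 28 response and normally has seen little or no response to assigned therapy, so it could select only on a baseline impression. Withholding a tube brings no quick release: results are due at up to 72 hours, whereas treatment starts within 24 hours, and Protocol 2.5.7 already provides for secondary therapy. Nothing in the documents shows that missingness would differ by arm. All of this stands, and it makes the larger shifts unlikely. It does not change the order of steps or supply the absent analysis.

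A reader might infer that the SAP has no check at all. That is not so: the by-arm missing count and the deviation list could reveal an imbalance. What they lack is the reason for each missing result and its effect on the estimate.

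A reader might also infer that a late sample counts as missing. The documents do not say so.

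Nor does SAP 2.8.1 promise an analysis of all randomised patients. It openly restricts the population to AA1/2 and uses intention to treat for classification by arm, so it would be too strong to say that a claimed protection is broken.

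Finally, about 20% of unscored patients would be expected to be AA3, and so properly outside the target population. Adding every unscored patient back does not recover the AA1/2 comparison exactly.

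**Conclusion.** The point holds as a structural gap, not as evidence of bias. Whether a score exists can depend on the arm, a missing score removes the patient from the main analyses, and no planned analysis shows what that does to the estimate.

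Under the assumed counts of 2, 4 or 6 unscored sirolimus patients and none on prednisone, the shift runs from 0 points (they respond like the rest), through 0.6 to 1.8 points (40% respond), to 1.9 to 5.5 points (none respond). The last range is a worst case and should not be read as the expected size. Bias arises only if missingness is related to both arm and outcome, and the missing rate is unknown.

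The trial is an estimation-only phase II study with no decision threshold, so this is a cheap improvement and not a flaw that undermines the design. The disagreement over whether unscored patients are described at all is a plain inconsistency and needs correcting in any case.

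**What to change.** 1. In Protocol 2.4.1 item 10, 4.2 and Appendix B, require the packed sample's barcode or courier tracking number to be entered in Segment A before AdvantageEDC displays the assignment. This reduces arm-dependent non-shipment but does not exclude it, because a number on file does not prove that the tube left the site.
2. In SAP 4.1, add a sensitivity analysis of Day 28 CR/PR in all randomised eligible patients except confirmed AA3, with missing-biomarker patients in their assigned arm. State that it includes some unscored AA3 patients and some who changed therapy. No new outcome data are needed: Protocol 2.5.2 already requires every patient to complete all assessments whatever the biomarker status.
3. Add the reason for each missing result (for example not shipped, lost or assay failure) to the existing by-arm count in Exhibit 1501-2.
4. Reconcile the synopsis and Protocol 2.5.2 and 5.1.3 with Protocol 3.3.8 and 5.2.7 and SAP 4.3.11.

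Rescoring from the stored pre-treatment serum is not a sound substitute. That sample is optional and shipped by the site, and its 48-hour window before therapy allows it to be drawn after the arm is known.

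The cost is one EDC field, one extra analysis, a recorded reason per missing result, and the text amendments.

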#### 4.2.1. Treatment

Treatment should be initiated as soon as possible after randomization. A maximum of 24 hours is allowable.

As per section 2.5.2, the patient's Ann Arbor results will be provided to the treating physician within 48-72 hours of study enrollment/randomization. Patients with AA1/2 status will continue on their randomized therapy. In contrast, patients with AA3 status and patients with missing biomarker results may continue on the randomized therapy, or another therapy per individual treating physician discretion.

#### 4.3. Study Monitoring

#### 4.3.1. Follow-up Schedule

The Follow-up Schedule for scheduled study visits is outlined in Table 4.3. A detailed description of each of the forms and the procedures required for forms completion and submission can be found in the Data Management Handbook and User's Guide.

**Follow-up Assessments**: The timing of follow-up visits is based on the date of randomization. Following randomization, the Transplant Center can print a Patient Visit Schedule listing target dates for assessments. Weeks 1-8 visits are primarily for acute GVHD scoring. The subsequent visits are for follow-up reports.

Assessment Time	Target Day  (Days Post-Enrollment)
1 week	7 days
2 weeks	14 days
3 weeks	21 days
4 weeks	28 days
5 weeks	35 days
6 weeks	42 days
7 weeks	49 days
8 weeks	56 days
90 days	90 days
6 months	180 days
12 months	365 days

# Table 4.3FOLLOW-UP SCHEDULE

Target day range =  $\pm 3$  days for Day 7 (subsequent visits through Day 56 must be scheduled weekly and within  $\pm 3$  days of target date). Target day range  $\pm 14$  days for Day 90 and 6 months; and  $\pm 28$  days for 12 months.

#### Criteria for Forms Submission:

All data for patients are recorded in the electronic Case Report Forms (eCRF) exclusively designed for the study. The Principal Investigator at each of the participating centers is responsible for complete, accurate and timely reporting of data.

Criteria for timeliness of submission for all study forms are detailed in the Data Management Handbook and User's Guide. Forms that are not entered into AdvantageEDC within the specified time will be considered delinquent. A missing form will continue to be requested either until the form is entered into the AdvantageEDC and integrated into the Data and Coordinating Center's (DCC) master database, or until an exception is granted and entered into the Missing Form Exception File, as detailed in the Data Management Handbook.

Corrections in the eCRF are to be conducted only by authorized personnel and may require authorization prior to implementation of corrections. However, all earlier entries are retrievable despite corrections. All corrections are recorded automatically concerning date, time point and person. Plausibility and completeness of the eCRF are verified by personnel at the Data Coordinating Center.

At all times, the Principal Investigators at the participating centers have full responsibility for ensuring accuracy and authenticity of all clinical and laboratory data entered on the eCRFs.

**Reporting Patient Deaths:** The Recipient Death Information must be entered into the webbased data entry system within 24 hours of knowledge of a patient's death. If the cause of death is unknown at that time, it need not be recorded at that time. However, once the cause of death is determined, the form must be updated.

